### **7.3.2 Dose Modification, Interruption or Discontinuation for Adverse Events**

The investigator and/or DSMB have the authority to reduce study medication dosage or discontinue study medication in a patient if situations develop that, in the opinion of the investigator or DSMB, would compromise the patient's safety or successful participation in the study (see Section 4.3 *Data Safety Monitoring Board* and Section 7.4 *Patient Discontinuation Criteria*). In particular, modifications in dosage or discontinuation of treatment will be instituted if any of the situations below apply.

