#### Level 3 Hepatotoxicity

Level 3 Hepatotoxicity is defined as follows:

- Patients who experience ALT or AST  $\geq 5 \times$  ULN on 2 separate occasions and at least 7 days apart.

Patients who experience confirmed Level 3 Hepatotoxicity will immediately interrupt study medication. The patient will return to the clinic for repeat blood tests including AP, bilirubin and International normalised ratio (INR) every 7 days until the aminotransferase levels have fallen  $< 3 \times$  ULN. Once this occurs, study drug dosing may be resumed at the dose level below that associated with Level 3 Hepatotoxicity.

If this dose level is tolerated without elevation of ALT or AST  $> 3 \times$  ULN, then this dose will be defined as the MTD. If aminotransferases increase  $\geq 3 \times$  ULN further dose reduction or interruption may be necessary consistent with the guidance provided in this protocol.

Elevations in ALT or AST  $> 3 \times$  ULN that persist despite dose reduction or interruption for  $\geq 4$  weeks will be reported to the DSMB by the sponsor (or its designee) immediately upon notification. Patients will be referred to a hepatologist for further work up.

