### Level 2 Hepatotoxicity

Level 2 Hepatotoxicity is defined as follows:

- Patients who experience ALT or AST 3.0 to 4.9 x ULN on 2 separate occasions and at least 7 days apart.

Patients who experience confirmed Level 2 Hepatotoxicity will have the dose of study medication reduced to the previous tolerated dose. The patient will return to the clinic for repeat blood tests including AP, bilirubin and INR every 7 days until the aminotransferase levels have fallen to <3 x ULN. Once this occurs, lomitapide dosing may be resumed at the dose level below that associated with Level 2 Hepatotoxicity.

If this dose level is tolerated without elevation of ALT or AST >3 x ULN, then this dose will be defined as the MTD. If aminotransferases increase >3 x ULN further dose reduction or interruption may be necessary consistent with the guidance provided in this protocol.

Elevations in ALT or AST >3 x ULN that persist despite dose interruption for  $\geq 4$  weeks will be reported to the DSMB by the sponsor (or its designee) immediately upon notification. Patients will be referred to a hepatologist for further work up.

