### **11.1.6 Adverse Events of Special Interest**

Adverse events of special interest (AESI) include the following:

- Hepatic, small bowel/intestinal, pancreatic and colorectal tumours
- Hepatic abnormalities
  - Elevations of hepatic transaminases resulting in discontinuation of lomitapide
  - Elevations of hepatic transaminases  $>3 \times$  ULN that persist despite dose reduction or interruption
  - Elevations of hepatic transaminases  $\geq 5 \times$  ULN
  - Symptomatic liver injury
  - Other hepatic evaluation and testing or any histology obtained from liver biopsy and imaging evaluations
- Gastrointestinal effects
  - Events leading to permanent treatment discontinuations
  - Hospitalisation due to gastrointestinal events
  - Events triggering additional investigations such as endoscopy

- Major congenital anomalies

Enhanced Pharmacovigilance will include systematically collecting and reviewing AESIs. In addition to reporting AESIs within 15 calendar days (see Section 11.5.2 *Reporting of Adverse Events of Special Interest*), they will be discussed in relevant safety aggregate reports.

The AESIs will also be diligently followed-up with the investigators using specialised query follow-up forms and they will also be identified as potential signals that will be reviewed during routine monthly signal detection activities (see Section 11.5.2 *Reporting of Adverse Events of Special Interest*).

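### The Level 2 liver rule orders a dose reduction, but its DSMB and hepatologist trigger counts only persistence after an interruption; at 2 mg the ordered reduction cannot be carried out

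*Protocol*

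**What the plan says.** Section 7.3.2 opens by saying that "modifications in dosage or discontinuation of treatment will be instituted if any of the situations below apply". The actions under it are therefore instructions to sites.

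- **Level 2, action.** A patient with confirmed ALT or AST of 3.0 to 4.9 x ULN "will have the dose of study medication reduced to the previous tolerated dose". Blood tests follow every 7 days until values are below 3 x ULN, after which "lomitapide dosing may be resumed at the dose level below that associated with Level 2 Hepatotoxicity". If values rise above 3 x ULN again, "further dose reduction or interruption may be necessary consistent with the guidance provided in this protocol".
- **Level 2, escalation.** The immediate DSMB report and the hepatologist referral apply to "Elevations in ALT or AST >3 x ULN that persist despite dose interruption" for 4 weeks or more.
- **Level 3.** Confirmed values of 5 x ULN or more lead to immediate interruption. The parallel escalation sentence covers elevations above 3 x ULN "that persist despite dose reduction or interruption for" 4 weeks or more.
- **AESI definition, section 11.1.6.** This lists transaminases above 3 x "ULN that persist despite dose reduction or interruption".
- **Doses.** Capsules come as 2, 5, 10 and 20 mg (section 7.2). Section 2.5 names 2 mg as the minimum strength. In Table 2, ages 5 to 10 and 11 to 15 start at 2 mg, and ages 16 to 17 start at 5 mg.

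**The concern.** The Level 2 trigger does not match the Level 2 action. A site that follows the rule exactly reduces the dose, and the clock for telling the DSMB and calling in a hepatologist starts only with a different action, one that is mentioned as possibly needed if values rise again. The DSMB can reduce or stop drug in an individual patient under 7.3.2, so whether it hears promptly matters.

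The second problem is that at the lowest dose the mandatory action does not exist. Because 7.3.2 requires some modification or discontinuation, leaving the child on unchanged 2 mg does not comply, yet Level 2 names nothing else to do. Two sites with the same confirmed values could act differently, one pausing and restarting, the other stopping for good. Section 2.6.1 describes lomitapide as a last resort for some of these children.

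**Working it through.** The Protocol gives no figure for this point to reproduce. The check is a comparison of texts and of the dose ladder.

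**Step 1. Action against trigger.**

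| | Ordered action | Persistence that escalates | Consequence |
|---|---|---|---|
| Level 2 | Reduction | After interruption only | Immediate DSMB report, hepatologist referral |
| Level 3 | Interruption | After reduction or interruption | Immediate DSMB report, hepatologist referral |
| AESI, 11.1.6 | (definition only) | After reduction or interruption | Report to Pharmacovigilance within 15 calendar days (11.5.2) |

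Level 2 is the level whose ordered action is a reduction, and it is the only row that leaves reduction out.

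**Step 2. Follow one child.** Confirmed Level 2 at 10 mg; dose reduced to 5 mg; values stay in the Level 2 range; no symptoms; bilirubin below 2 x ULN; no interruption. Count weeks from the reduction.

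- With the Level 3 wording, the report and referral fall due at week 4.
- With the Level 2 wording, they fall due at week d + 4, where d is the number of weeks from reduction to interruption. The Protocol does not give d. For assumed values d = 1, 2 and 4 the result is 1 + 4 = 5, 2 + 4 = 6 and 4 + 4 = 8 weeks. With no interruption they never fall due.
- The sentence allowing further reduction or interruption speaks of values that increase, so it does not clearly reach a value that never came down.

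**Step 3. Which cases another rule catches.** The opening rule of the Biochemical Hepatobiliary Guidelines requires discontinuation, an immediate DSMB report and hepatologist referral when aminotransferase elevations come with symptoms of liver injury or bilirubin of 2 x ULN or more. The gap is therefore confined to children with all of the following: confirmed Level 2, persistence above 3 x ULN for at least 4 weeks on the reduced dose, no interruption, no such symptoms, and bilirubin below 2 x ULN.

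**Step 4. The dose ladder.** Section 7.2 has each patient take 1 to 3 capsules once daily, so the smallest daily dose is 1 x 2 mg = 2 mg.

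- Ages 5 to 10: 2, 2, 5, 10, 20 mg, so 2 mg from D0 until Week 8.
- Ages 11 to 15: 2, 5, 10, 20, 40 mg, so 2 mg from D0 until Week 4.
- Ages 16 to 17: start at 5 mg, from which the general rule in 7.3.1 on intermediate doses leaves room for 2 mg.

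Below 2 mg the next step is 0 mg, which is an interruption and not a reduction. Neither a previous tolerated dose nor an intermediate dose exists. The case arises at the start of treatment in ages 5 to 15 and again in anyone reduced to 2 mg later.

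**Step 5. Restart at 2 mg.** The Level 2 resumption sentence points to the level below, and there is none. Section 7.3.1 allows re-challenge once the cause has resolved, at least 4 weeks after a dose reduction, except in Hy's law or comparable cases. Its definition of the maximum tolerated dose may include a re-challenged level. These rules bear on the question, but they do not name a child who was at the lowest dose and could not be reduced.

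**The case against.** The strongest reply is that several other provisions surround this rule.

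- Section 7.3.1 lets the investigator reduce or hold the dose, and 7.3.2 lets the investigator or the DSMB reduce or stop it. Weekly tests continue.
- The AESI category has no 4-week minimum, so it can apply earlier than the DSMB clause. Section 11.5.2 adds specialised follow-up, monthly signal review and expedited reporting of specific hepatic abnormalities. The sponsor side receives the AESI report, and the sponsor or its designee is the party that notifies the DSMB.
- The DSMB reviews safety periodically and as needed (4.3), and biopsy is to be considered for Level 2 elevation lasting 6 months or more.
- Section 2.6.3 says the algorithm follows an approach agreed with a DSMB hepatologist and used in the adult pivotal study.

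All of this stands as mitigation. None of it obliges anyone to tell the DSMB immediately or to refer the child after a failed reduction, and none gives sites a common instruction at 2 mg.

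A reader might infer four stronger points, which the documents do not support.

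- **That all of the roughly 45 children are exposed to the trigger gap.** Step 3 shows a much narrower group. The symptoms that activate the other rule include nausea, vomiting and abdominal pain, which 2.6.3 lists among the most common adult adverse events.
- **That the share of liver tests taken on 2 mg measures the risk.** With three equal groups of 15 and no dose holds, that share is (15 x 2 + 15 x 1)/(45 x 6) = 45/270 = 16.7% of Efficacy Phase tests, but 45/(45 x 18) = 45/810 = 5.6% of tests to Week 104. Neither is a probability of an event.
- **That the DSMB would never learn of such a child.** Periodic review and the AESI route make that too strong; what is missing is the immediate report.
- **That Level 3 has the same fault.** Level 3 orders an interruption, which can be carried out at any dose, and its trigger names both actions.

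**Conclusion.** Wrong as written: the Level 2 escalation trigger does not match the action that Level 2 orders. A confirmed Level 2 elevation that persists on the reduced dose, without symptoms, with bilirubin below 2 x ULN and without an interruption, prompts no immediate DSMB report and no hepatologist referral, and is reported only as an AESI. The 2 mg gap is a smaller, related defect in the same rule: the ordered step is impossible and no alternative action is ordered.

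The size cannot be put as a number of children, because the Protocol gives no rate of confirmed Level 2 in this age range. The adult pivotal study gives context only: 10 of 29 had ALT or AST above 3 x ULN at least once, at maximum tolerated doses of 5 to 60 mg, and none stopped permanently for liver tests. Those rises were not confirmed twice, and they say nothing about 2 mg.

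The conclusion rests on reading the hepatologist sentence at the end of Level 2 as belonging to the persistence sentence before it, as its position suggests. It also reads symptoms and raised bilirubin in the opening rule as alternatives. A reader might infer an effect on the primary analysis; nothing here supports one, and none is claimed for the Week 24 result.

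**What to change.** In section 7.3.2, Level 2:

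1. In the persistence sentence, name dose reduction alongside dose interruption, as Level 3 and 11.1.6 already do.
2. After the reduction order, add: At 2 mg, where no lower dose exists, study medication is interrupted until ALT/AST is <3 x ULN. Follow it with one line stating whether 2 mg may then be restarted.

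Keep the sentence on resuming at the level below. It is awkward after a reduction, but it is the only Level 2 rule on the restart dose for a child above 2 mg who has been interrupted. Level 3 needs no change for this point.

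The cost is an amendment of a few sentences, submitted to ethics committees and regulators under section 15, and possibly a few more DSMB reports and hepatologist referrals. Visits, tests and sample size do not change.

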### Level 1 Hepatotoxicity

Level 1 Hepatotoxicity is defined as follows:

- Patients who experience ALT or AST 1.1 to 2.9 x ULN.

No dose modification will be required.

## **Considerations for Liver Biopsy and Histopathological Guidelines**

### Considerations for Liver Biopsy

A percutaneous liver biopsy should be considered for persistent Level 2 Hepatotoxicity defined as AST or ALT  $\geq 3$  x ULN for  $\geq 6$  months but can also be performed at the discretion of the investigator.

### Histopathological Hepatobiliary Guidelines

If a patient undergoes a liver biopsy and the specimen shows the following features, the patient will be discontinued from the study and followed by a hepatologist:

- Type 3 non-alcoholic steatohepatitis (NASH) characterised by fat accumulation and ballooning degeneration, or
- Type 4 NASH characterised by fat accumulation, ballooning degeneration, and either Mallory's hyaline or fibrosis.

Patients with fatty liver alone (Type 1 NASH) or fat accumulation and lobular inflammation but without ballooning degeneration and/or Mallory's hyaline or fibrosis (Type 2 NASH) will continue on study medication, and discontinuation will be dictated by biochemical criteria.

### **Creatinine Kinase Monitoring and Evaluation**

If CK values are found to be elevated >5 x ULN on routine testing, the patient should be questioned about muscle symptoms.

A study site physician should be alerted to the occurrence of unexplained muscle symptoms and any CK values >5 x ULN, and must take immediate action if CK is >10 x ULN.

If CK values are >5 x ULN with muscle symptoms or >10 x ULN with or without muscle symptoms the following steps should be taken:

- Clarify the nature, duration and intensity of any muscle symptoms.

- Review possible predisposing factors, such as: unaccustomed exercise, heavy alcohol intake, viral illness (consider performing serology), concomitant medication and consider diagnosis of other conditions which cause myopathy.
- Physical examination for muscle tenderness, weakness and rash.
- Measure CK again within a few days.
- Measure serum creatinine.
- Urine dipstick.
- Arrange to review the patient again in 4 to 10 days, or earlier if symptoms of myopathy appear or worsen, or if the urine becomes very dark.

Discontinue study medication for CK values  $>10 \times \text{ULN}$  with or without muscle symptoms.

For CK values 5 to 10  $\times \text{ULN}$ :

If asymptomatic, or if symptomatic but alternative explanation exists, symptoms should be followed and CK levels tested weekly until it is no longer a medical concern or symptoms worsen and meet criteria for any of the above.

If symptomatic, and no alternative explanation exists, withhold therapy.

Throughout the study, patients should be instructed to promptly report any unexplained muscle pain or weakness, particularly if associated with malaise or fever. If this should occur, CK should be measured as soon as possible.

### **Dose Modification Based on Weight Loss**

Weight will be measured using a consistent approach at Screening and at each visit after the Run-in Period (i.e., child/adolescent always weighed in same amount of clothing, either in underwear, hospital gowns or by subtracting the weight of clothes). Patients of normal or below normal body weight based on gender and age-specific WHO growth charts (see Appendix 4 *WHO Growth Charts*) with weight loss  $>3\%$  since the previous visit will meet with the dietitian for further instruction. Patients with below normal body weight any time during the study who continue to lose weight while on study medication despite all appropriate measures taken to correct for the weight loss and who are deemed to be at clinical risk in the judgment of the treating investigator should discontinue study drug and be followed until an acceptable stable weight is reached as judged by the investigator.

#### **7.3.3 Dose Modification for Concomitant Medication**

##### **Weak Cytochrome P450 (CYP) 3A4 Inhibitors**

Medicinal products that induce CYP 3A4 would be expected to increase the rate and extent of metabolism of lomitapide. CYP 3A4 inducers exert their effect in a time-dependent manner, and may take at least 2 weeks to reach maximal effect after introduction. Conversely, on discontinuation, CYP 3A4 induction may take at least 2 weeks to decline.

Co-administration of a CYP 3A4 inducer is expected to reduce the effect of lomitapide. Any impact on efficacy is likely to be variable. When co-administering CYP 3A4 inducers (i.e., aminoglutethimide, naftacin, non-nucleoside reverse transcriptase inhibitors, phenobarbital, rifampicin, carbamazepine, pioglitazone, glucocorticoids, modafinil and phenytoin) with lomitapide, the possibility of a drug-drug interaction affecting efficacy should be considered.

Strong or moderate cytochrome CYP 3A4 inhibitors are not permitted during the study as described in Section 7.6.3 Non-Permitted Concomitant Medication, Food or Substances.

Weak cytochrome CYP 3A4 inhibitors are only permitted during the Safety Phase of the study, but lomitapide should be administered 12 hours apart. If atorvastatin is given concomitantly, it should be administered in the morning to separate it from lomitapide dosing by 12 hours. In case it is not possible to administer atorvastatin and lomitapide 12 hours apart, the lomitapide

dose should be reduced by half, as the lomitapide dose can be reduced from the MTD due to tolerability or safety issues during the 80-week Safety Phase. After a minimum period of 4 weeks following dose reduction the patient can be re-challenged with a higher dose of lomitapide once these issues resolve (i.e., if atorvastatin can be administered 12 hours apart or if atorvastatin is discontinued), but the dose during the Safety Phase cannot exceed the MTD established during the Efficacy Phase unless eligibility for exceptional dose escalation is met (described in Section 7.3.1 *Dose Escalation, Dose Reduction and Re-challenge*).

